Overweight and obesity are defined as abnormal or excessive fat accumulation that presents a risk to health. A body mass index (BMI) over 25 is considered overweight, and over 30 is obese.¹ The definition of overweight and obesity is abnormal or excessive fat buildup that poses a health risk. Over 25 is classified as overweight, and over 30 as obese based on body mass index (BMI). The worldwide burden of illness report from 2017 shows that the problem has reached epidemic proportions, with over 4 million deaths annually attributable to being overweight or obese.² Bariatric surgery is the most effective treatment of morbidly obese patients to allow substantial, sustained weight loss and to improve or resolve obesity-associated comorbidities, thereby reducing mortality. According to US practice guidelines, patients qualify for bariatric surgery with a body mass index of 35 kg/m² and associated comorbidities, or a body mass index of 40 kg/m², after failure of conservative weight loss measures. Currently, the established procedures in the United States are the laparoscopic Roux-en-Y gastric bypass, adjustable gastric banding, sleeve gastrectomy, and biliopancreatic diversion with duodenal switch². Although bariatric surgeries are generally safe and effective, they can have deadly side effects that need to be promptly handled. Leaks, stenosis, bleeding, and venous thromboembolic events (VTE) are examples of early complications. Postoperative bleeding that requires intervention occurs in up to 11% of cases in both the RYGB and SG³. Fortunately, 85% of patients are likely to stop without surgical intervention⁴. Individuals with metabolic syndrome X are more likely to experience bleeding. Establishing an appropriate venous access, performing crystalloid resuscitation, blood product transfusions, serial hematocrits, hemodynamic monitoring, correcting any coagulopathies, and ceasing to administer VTE chemoprophylaxis are all examples of usual supportive care that should be started right away. In the early postoperative phase, a skilled endoscopist can safely assess an anastomosis and administer therapeutic endoluminal treatments, such as clips or epinephrine injections, as first-line therapy⁵. Emergency surgical management is required if non-operative management fails due to hemodynamic instability. After an SG, bleeding typically occurs at the staple line, however splenic damage is also a possibility. The anastomoses are likely the sites of bleeding after RYGB, however intra-abdominal hemorrhage from the spleen, mesentery, and omentum may also occur. The surgeon must check for bleeding sites inside the gastric remnant, the biliopancreatic limb, and the Roux limb if there isn't an obvious site detected.⁶ Bleeding in bariatric surgery can also occur as a late complication. Bleeding Mild to moderate bleeding from marginal ulcers occurs in 5% of patients; massive hemorrhage is substantially less common⁷. Like any patient with upper gastrointestinal bleeding, the patient may present with hematemesis, melena or hematochezia, and syncope or near-syncope. The primary goals of initial care should be intravenous proton pump inhibitors, reversal of antiplatelet or anticoagulant medication, and resuscitation with crystalloid or blood products, if necessary. Upper endoscopy is typically used for therapy and diagnosis. The GJA site is frequently the site of bleeding, most of which may be managed with routine endoscopic procedures. In one trial, just 4% of individuals with bleeding marginal ulcers needed surgery.⁸ Tranexamic acid (TXA) stops fibrin's enzymatic breakdown, which lowers blood loss. In order to reduce bleeding and the need for blood transfusions, it is frequently used during surgery. A multicenter, randomised, placebo-controlled experiment (CRASH-2 trial) published its findings in 2011 and demonstrated that TXA (1 g loading dosage over 10 min, followed by an 8-hour infusion of 1 g) safely lowers mortality in patients with bleeding trauma. Regardless of baseline risk, starting TXA treatment within three hours of damage reduces the risk of bleeding fatality by approximately one-third. Restricting its application to individuals with serious injuries or a diagnosis of "hyperfibrinolysis" would lead to thousands of preventable deaths. Tranexamic acid (TXA) stops fibrin's enzymatic breakdown, which lowers blood loss. In order to reduce bleeding and the need for blood transfusions, it is frequently used during

surgery. A multicenter, randomised, placebo-controlled experiment (CRASH-2 trial) published its findings in 2011 and demonstrated that TXA (1 g loading dosage over 10 min, followed by an 8-hour infusion of 1 g) safely lowers mortality in patients with bleeding trauma. Regardless of baseline risk, starting TXA therapy within three hours of damage lowers the chance of bleeding fatality by almost one-third.⁹ Extensive randomized studies in postpartum hemorrhage (20 060 patients) and trauma (20 211 patients) demonstrate that tranexamic acid dramatically lowers bleeding fatalities without raising the risk of thrombosis.¹⁰ It was first introduced to clinical practice for the management of patients with bleeding disorders, especially adapted to reduce bleeding in hemophiliacs undergoing oral surgical intervention¹¹. Over the past ten years, tranexamic acid (TXA) has garnered increasing attention due to its potential to optimize post-operative bleeding; yet, its exact role in bariatric surgery remains unclear¹². Our study aims at evaluating the role of tranexamic acid in bariatric surgery since, The effect of conservative therapy using tranexamic acid for postoperative hemorrhage after bariatric surgery is still very much a novel technique¹³. However, Intravenous tranexamic acid at the time of laparoscopic sleeve gastrectomy is associated with a significant reduction of post-operative bleeding with no observed differences in thromboembolic events or mortality¹⁴.

6. Objectives:(describe specific objectives or hypotheses behind the study)

Evaluate the role of tranexamic acid in preventing and decreasing intra-operative and post-operative in bariatric surgery.

7. Study Design:

A- Nature of the study

- Prospective study
- Retrospective study

B- Design of the study: (Please insert ✓ in front of the suitable design)

1-	Case series	
----	-------------	--

2-	Qualitative	
3-	Survey	
4-	Cross sectional analytic	
5-	Case-control	
6-	Cohort (Longitudinal)	
7-	Randomized Clinical Trial	
8-	Non-randomized clinical trial	
9-	Animal study	
10-	Cellular study	

- **Other study design:**

Please describe:

8. Study Methods

- **Population of study:** (Please provide all details regarding participants including gender, age range and disease conditions. Indicate if this protocol involves children, prisoners, pregnant women or cognitively impaired or mentally disabled subjects. Also indicate if participants will be divided into groups and mention the characteristics of and number of participants in each group adequately)
 - Patients undergoing bariatric surgery at Kasralainy School of Medicine between January 2024 and August 2024
- **Study location:** (Please provide where the study will be conducted and from where study participants will be recruited)
 - Kasralainy Hospital, Cairo University
- **Inclusion criteria:**
 - Age 18-60 years at time of surgery.
 - Body mass index (BMI) of more than 35 kg/m² or more than 30 kg/m² with a major co-morbidity associated with obesity.
- **Exclusion criteria:**
 - Previous history of DVT
 - Have experienced a tranexamic acid adverse reaction
 - Bleeding tendency
 - Administration of anti-coagulants or anti-platelets
 - Coagulopathy disease
 - Uncontrolled hypertensive

- **Methodology in details:**(the description should be chronological starting with randomization method in detail if RCT, group allocation and characteristics of each group. Also indicate what would be done to participants initially and at follow-up visits including the follow-up duration, if applicable)

Patients will randomly allocated (1:1) in two groups, group A and group B, one week before surgery by the coordinating researcher via computer-generated variable block randomization software by Ciwit BV (Castor EDC©). The patient, surgical team, and anesthesia team were blinded for treatment allocation. The coordinating researcher and hospital pharmacologist were unblinded to properly prepare the infusion bags for each individual patient. Both were not involved in the surgical procedure nor in the follow-up. Patients in each group will have proper history taking, routine pre-operative assessment. The intervention group (B) will receive a single dose of 1500-mg TXA (Cyklokapron©) during the induction of the procedure. TXA will be administered intravenously, dissolved in 100-ml sodium chloride (NaCl) 0.9% in a time frame of 15–30 min, with a maximum of 100 mg/min. The control group (A) will receive a placebo during the induction of the procedure. The placebo infusion contains 100-ml NaCl 0.9%, which will be administered similarly. Both groups will be operated on within the same range of blood pressure. Assessment of intra-operative bleeding will be through the number of clips used on the staple line. To determine postoperative hemoglobin levels, a blood sample (one EDTA tube) will be obtained at day one postoperatively by venipuncture and analyzed in the hospital's clinical chemistry laboratory according to standard procedures. Patients will be discharged at day 3 post-op, on anti-coagulant 40mg/24H for two weeks. Follow up will be done after 30 days. Duple will be done to assess the incidence of DVT.

- **Intervention:**

- Diagnostic intervention (please describe):
- Therapeutic intervention (please describe):
- No intervention

- **Does the research involve?**

- Human participants
- Biological samples/Tissues
- Identifiable private data/Information

- **Type of consent of study participants:**

- Written consent
- No consent needed (Please justify)

- **Potential risks:**

(Please mention all risks involved even mild ones as pain, discomfort, chance of infection or psychological effects)

- 1-
- 2-
- 3-

- **Confidentiality of data:** (Please explain how privacy and confidentiality of data and records will be maintained)

9- Study outcomes:

- **Primary outcomes** (Most important measurable outcomes)

- 1- Number of cases of bleeding in each group either intra-operative or post-operative
- 2- definition of bleeding: hemoglobin drop >1

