Plication of Fascia Transversalis and Its Role in Reduction of Seroma Formation Post Laparoscopic Transabdominal Preperitoneal Repair of Direct Inguinal Hernia

A Thesis Submitted For Partial Fulfillment of MSc Degree of General Surgery

By

[name] [name]

Ethical Approval Number: MS 204-2024

Supervisors

[name]. [name]
Professor of General Surgery
Faculty of Medicine, Cairo University

[name] [name]
Lecturer of General Surgery
Faculty of Medicine, Cairo University

[name] [name]
Lecturer of General Surgery
Faculty of Medicine, Cairo University

Faculty of Medicine
Cairo University
2025

Statistical Analysis

Data are analyzed using SPSS version 21. Descriptive statistics are presented as means with standard deviation for continuous variables and frequencies with percentages for categorical variables. Comparisons between groups are made using:

- Chi-square test or Fisher 's exact test for categorical data.
- Student ' s t-test for normally distributed continuous variables.
- Mann-Whitney U test for non-normally distributed data.
- Paired t-test for preoperative and postoperative comparisons within each group.
- Pearson or Spearman correlation tests to assess relationships between variables.

A p-value < 0.05 is considered statistically significant.

Ethical Considerations

This study is conducted in accordance with the Declaration of Helsinki and is approved by the Institutional Review Board (IRB) of Cairo University. Written informed consent is obtained from all participants prior to enrollment. Patients' confidentiality is maintained, and their data are anonymized. No financial incentives are provided, and participation is voluntary. Potential risks, including coagulation alterations and allergic reactions, are clearly explained to the patients.

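### If more than one bariatric procedure is performed, the unadjusted analysis leaves procedure-related variation in the comparison, costing precision mainly for clip count and duration of surgery

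*Protocol*

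**What the plan says.** - **Population** (Protocol, section 8, Population of study): "Patients undergoing bariatric surgery at Kasralainy School of Medicine between January 2024 and August 2024". No inclusion or exclusion criterion names a procedure.
- **Bleeding by procedure** (Protocol, background text before section 6): for sleeve gastrectomy (SG), "After an SG, bleeding typically occurs at the staple line"; for Roux-en-Y gastric bypass (RYGB), "The anastomoses are likely the sites of bleeding after RYGB". The only rate by procedure is a shared ceiling: "Postoperative bleeding that requires intervention occurs in up to 11% of cases in both the RYGB and SG".
- **Allocation** (Protocol, section 8, Methodology in details): 1:1, one week before surgery, using "computer-generated variable block randomization software". No stratification factor is stated.
- **Outcomes**: in the same section, "Assessment of intra-operative bleeding will be through the number of clips used on the staple line". Section 9 makes the number of bleeding cases the primary outcome, defined by a haemoglobin drop above 1 with no unit, and lists duration of surgery as secondary.
- **Analysis**: sections 10 and 11 of the protocol give no sample size and no analysis text. The SAP, under Statistical Analysis, offers "Chi-square test or Fisher 's exact test for categorical data", the t-test or Mann-Whitney test for continuous data, paired t-tests and correlations. It has no stratified or covariate-adjusted analysis.

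**The concern.** The planned procedure should normally be known when patients are allocated a week before surgery, so it is a baseline variable that needs no new data. Two of the quantities to be compared plausibly depend on it whatever tranexamic acid does. A clip count on the staple line follows the bleeding site that the protocol gives for sleeve, not the one it gives for bypass. Operating time is also likely to differ between operations.

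Variable blocks balance the number of patients per arm, not the mix of procedures within each arm. If the trial is small, the arms can differ noticeably in case mix. The listed tests would neither remove that difference nor use procedure to reduce residual variance.

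**Working it through.** The documents state no sample size, power or effect size, so there is no planned figure to reproduce. The patients per arm (n), the sleeve share (p) and all gaps between procedures below are assumptions, shown over a range.

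**Step 1: chance imbalance in procedure.** If procedure is unrelated to the blocks, the SD of the between-arm difference in sleeve share is sqrt(2p(1-p)/n). With p = 0.5 and n = 50 this is sqrt(0.5/50) = 0.10, and the 95% limit is 1.96 x 0.10 = 0.196.

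**Step 2: shift in the result.** Shift = imbalance x gap in the outcome between procedures. At n = 50 with a 10-point gap in bleeding risk: 0.196 x 0.10 = 0.020. With a 20-point gap: 0.196 x 0.20 = 0.039. With no gap: 0.

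| n per arm (p = 0.5) | 95% imbalance limit, points | Chance of at least 10 points | Bleeding shift at the limit for a gap of 0 / 5 / 10 / 20 points | Clip shift at the limit for a 2-clip gap |
|---|---|---|---|---|
| 30 | 25 | 0.52 | 0 / 1.3 / 2.5 / 5.1 | 0.51 |
| 50 | 20 | 0.37 | 0 / 1.0 / 2.0 / 3.9 | 0.39 |
| 100 | 14 | 0.18 | 0 / 0.7 / 1.4 / 2.8 | 0.28 |
| 200 | 10 | 0.05 | 0 / 0.5 / 1.0 / 2.0 | 0.20 |

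With a 70% sleeve share the limits are slightly smaller: 23, 18, 13 and 9 points.

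**Step 3: is the test invalid?** In 4,000 simulated trials per setting with no treatment effect, n of 30, 50 or 100, and a normal outcome differing between procedures by 0, 1 or 2 within-procedure SDs, the unadjusted t-test rejected in 0.049 to 0.054 of trials. Its overall error rate holds.

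**Step 4: what adjustment gains for a continuous outcome.** The variance of the unadjusted estimate was 1.23 to 1.25 times that of the adjusted estimate for a 1 SD gap, and 1.92 to 2.09 times for a 2 SD gap. Among trials at n = 50 with an imbalance of at least 20 points (about 6% of trials), the unadjusted test rejected in 0.17 (1 SD) or 0.36 (2 SD), and the adjusted test in 0.05 or 0.07. At n = 30 the figures were 0.11 and 0.21 unadjusted, 0.05 and 0.06 adjusted. The conditional figures at n = 50 rest on about 205 trials each. Those at n = 100 rest on fewer than 20 and are not used.

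**Step 5: what adjustment gains for bleeding.** At a 50:50 mix, with assumed rates of 6% and 16%, procedure explains 0.0025/0.098 = 2.6% of outcome variance. With 20% and 40% it explains 0.01/0.21 = 4.8%. Ignoring it widens the confidence interval by about 1.3% and 2.5%. The standard errors of the risk difference at n = 50 are sqrt(2 x 0.11 x 0.89/50) = 6.3 points and sqrt(2 x 0.30 x 0.70/50) = 9.2 points, so shifts of 2.0 and 3.9 points are about 0.3 and 0.4 standard errors. At a fixed 20-point imbalance and n = 50, the unadjusted two-proportion test rejected in 0.05 (equal rates), 0.06 (6% and 16%) and 0.08 (20% and 50%). At n = 100 it rejected in 0.05, 0.07 and 0.13, but an imbalance that large then has a chance of only 0.006.

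**The case against.** The case against making much of this is substantial.

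- **Different rates are not shown.** A reader might infer from the different bleeding sites that procedure is a strong, known predictor of bleeding. The documents do not support that: the only rate is the same ceiling for both procedures. It concerns bleeding that needs intervention, so it does not prove that a haemoglobin drop above 1 is equally common in both, but nothing shows a difference either. This stands, and the range of shifts must start at zero.
- **There is no bias.** A reader might also infer that case mix could pass for a treatment effect more often than the p-value allows. Over all randomisations it does not (Step 3). What remains is lost precision, and error rates that are raised only in trials that happen to be badly imbalanced.
- **Pooling is inferred.** No text says which procedures will be done, and a mainly sleeve series would fit the staple-line measure. Silence about stratification is likewise not a statement that there is none. This stands, so the point is conditional on more than one procedure being performed.
- **Clips raise a separate validity problem.** A staple-line count does not capture bleeding at an anastomosis, and adjusting for procedure cannot repair that. Clip count is also not listed as a separate outcome in section 9. Adjustment addresses only the variation in the count.
- **It is late.** The protocol places surgery between January and August 2024, and the SAP's title page is dated 2025. Stratified randomisation is probably no longer possible, and an adjustment chosen after unblinded data have been seen would be post hoc.

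None of this removes the case for pre-specified adjustment, which uses a baseline fact and has little downside.

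**Conclusion.** The point holds as a modest matter of precision, conditional on more than one procedure being performed. Eligibility is open to any bariatric surgery, no stratification factor is stated, and every listed test is unadjusted.

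The gain is mainly for clip count and duration of surgery. If these differ between procedures by an assumed 1 to 2 SDs, the unadjusted estimate has about 1.2 to 2 times the variance of the adjusted one. For haemoglobin-defined bleeding the effect is small and may be nil: at an assumed 50 per arm and 50:50 mix, the shift at the 95% imbalance limit is 0 points if the rates are equal, about 2 for a 10-point gap and about 4 for a 20-point gap. Every one of these sizes depends on assumed n, case mix and gap, because the documents give none of them. The change is worth making but is not critical to the validity of the trial.

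**What to change.** 1. Name the eligible procedures in the protocol. If only one is performed, say so; the remaining steps then fall away.
2. Otherwise, before any unblinded analysis, pre-specify for bleeding a Mantel-Haenszel risk difference and a CMH test stratified by planned procedure (sleeve versus bypass/other).
3. For clip count and duration, include planned procedure as a covariate or use a rank test stratified by procedure.
4. Keep the unadjusted tests as sensitivity analyses.
5. If data have already been seen unblinded, label the adjusted analysis post hoc.
6. Add procedure as a randomisation stratum only if patients remain to be allocated.

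**Cost:** no new data, but the SAP contains no models at present, so a few analyses must be written in rather than one phrase changed. Rare procedures must be pooled into one stratum.

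### The only specifically intra-operative bleeding measure is a staple-line clip count, which misses other sites and other means of haemostasis; day-one haemoglobin covers these only in part

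*Protocol*

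**What the plan says.** Five places in the protocol bear on this point.

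- **Section 6, Objectives:** "Evaluate the role of tranexamic acid in preventing and decreasing intra-operative and post-operative in bariatric surgery". The noun is missing, but the context makes it bleeding. The aim covers both phases and bariatric surgery in general.
- **Section 8, Population of study:** "Patients undergoing bariatric surgery at Kasralainy School of Medicine between January 2024 and August 2024". Neither this line nor the eligibility criteria restrict the type of procedure.
- **Section 8, Methodology in details:** "Assessment of intra-operative bleeding will be through the number of clips used on the staple line". No blood-loss volume, transfusion, or haemostasis at another site or by another means is listed here or among the outcomes. For haemoglobin, "a blood sample (one EDTA tube) will be obtained at day one postoperatively by venipuncture".
- **Section 9, Study outcomes:** the primary outcome is "Number of cases of bleeding in each group either intra-operative or post-operative", followed by "definition of bleeding: hemoglobin drop >1".
- **Background, before section 6:** for sleeve gastrectomy, "After an SG, bleeding typically occurs at the staple line, however splenic damage is also a possibility". For bypass, "The anastomoses are likely the sites of bleeding after RYGB, however intra-abdominal hemorrhage from the spleen, mesentery, and omentum may also occur".

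The SAP's Statistical Analysis section lists general tests and a 0.05 significance level. It names no bleeding measure.

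**The concern.** The measure covers one site and one means of control, while the objective and the eligible population are wider. Suppose bleeding occurs at an anastomosis or in the mesentery, or a staple-line ooze is stopped without a clip. The clip count is then the same as for a dry operation.

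At stake is how the intra-operative result can be read. A finding of no difference in clips could mean that TXA does not reduce operative bleeding. It could also mean that the bleeding it reduced was elsewhere, or was stopped by other means. Nothing else recorded in theatre would tell these apart, and what is not written down at operation may not be recoverable later.

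**Working it through.** **Step 1. What each measure can see.** The claim rests on no figure in the documents, so the first check sets the two protocol measures side by side.

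| Event | Staple-line clip count | Haemoglobin rule, day one |
|---|---|---|
| Operative bleed on staple line, clipped | Counted | Only if the drop exceeds 1 |
| Operative bleed on staple line, controlled without a clip | Not counted | Only if the drop exceeds 1 |
| Operative bleed at anastomosis, mesentery, omentum or spleen | Not counted | Only if the drop exceeds 1 |
| Early post-operative bleed before the sample | Not counted | Only if the drop exceeds 1 |

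Two things follow. The last three rows can leave identical records, so the data cannot say which phase the bleeding came from. And a bleed in row two or three that is controlled before haemoglobin falls by more than 1 leaves no trace on either measure.

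**Step 2. Fit with the eligible procedures.** For sleeve gastrectomy, the background supports the staple line as the typical site. For bypass, it puts the likely sites at the anastomoses. A bypass also has staple lines, so the count will capture some of its bleeding. The fit therefore depends on the procedure mix, which the documents do not give.

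**Step 3. Illustration of size.** Section 10 of the protocol (sample size) is blank, so there is no planned figure to reproduce. The following inputs are assumptions:

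- true control risk of an operative bleed: 5%, 11% or 20%. The 11% borrows the background's upper figure for post-operative bleeding needing intervention and is not an intra-operative rate;
- TXA halves the risk;
- the count is reduced to yes or no per patient, which the protocol does not specify;
- the measure sees a share s of bleeds, equal in both arms, with no false positives.

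The 1:1 allocation is from the protocol and the 0.05 level from the SAP. A two-sided test is assumed, with 80% power when s = 1.

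Visible risks are p1 = s × control risk and p2 = s × TXA risk. With m the mean of p1 and p2:

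- n per arm = [1.96√(2m(1−m)) + 0.8416√(p1(1−p1) + p2(1−p2))]² / (p1−p2)²
- power = Φ{[(p1−p2)√n − 1.96√(2m(1−m))] / √(p1(1−p1) + p2(1−p2))}

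Worked case, 20% v 10% with s = 0.5. The visible risks are 10% v 5% and m = 0.075. Then n = (0.7301 + 0.3121)² / 0.05² = 435 after rounding up. With the 199 per arm that suffice at s = 1, power = Φ[(0.7053 − 0.7301) / 0.3708] = Φ(−0.067) = 0.473.

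| s | 5% v 2.5%: n per arm; power at 906 | 11% v 5.5%: n per arm; power at 392 | 20% v 10%: n per arm; power at 199 |
|---|---|---|---|
| 1 | 906; 80% | 392; 80% | 199; 80% |
| 0.75 | 1,220; 67.5% | 535; 67.0% | 278; 65.9% |
| 0.5 | 1,848; 50.1% | 820; 49.0% | 435; 47.3% |
| 0.25 | 3,731; 28.1% | 1,676; 27.2% | 906; 25.8% |

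Under these assumptions the risk ratio stays at 0.5 for every s. What is lost is sensitivity: the visible absolute difference shrinks in proportion to s. The table applies to an analysis of the clip measure alone, not to the primary outcome.

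**The case against.** A reader might infer that bleeding off the staple line goes wholly unrecorded and that the intra-operative half of the objective is left unanswered. The documents do not support that. The haemoglobin definition sits directly under a primary outcome that names intra-operative bleeding, and it has no site restriction. A patient with substantial mesenteric or splenic loss adds nothing to the clip count but can still be a bleeding case. Because the primary outcome pools the two phases, it does not need them separated. This part of the objection stands: the objective is answered in part, through clips for the staple line and through haemoglobin, imperfectly, for total loss.

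Three further points also stand.

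- The site list in the background concerns post-operative complications. Its use for operative bleeding is an inference, not something the protocol states.
- For sleeve gastrectomy the background favours the chosen measure.
- The documents do not describe haemostatic technique, so control by suture or energy is a plausible scenario and not a documented practice. The surgical team is blinded, so clip use that differs by arm for reasons other than bleeding is not expected.

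None of this closes the gap. A day-one sample mixes operative with early post-operative loss, and a bleed found and controlled in theatre may not lower haemoglobin by more than 1. Such an event is what an intra-operative measure should record.

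**Conclusion.** The point holds in a limited form. The one measure specific to the operation covers a single site and a single means of control, in a trial open to any bariatric procedure. By reasonable inference it misses some operative bleeding. Day-one haemoglobin recovers part of that but cannot attribute it to the operation. This is a stated measurement rule that is too narrow for the objective; it does not invalidate the primary outcome.

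The size cannot be established. It depends on the procedure mix and on the share of bleeds off the staple line or controlled without clips, and the documents give neither. The power figures show direction and scale under assumed values only. The protocol also does not say how a clip count becomes a bleeding case, so the clip measure in section 8 and the haemoglobin definition in section 9 need to be reconciled.

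**What to change.** In section 8, Methodology in details, replace the staple-line clip count as the intra-operative measure with haemostatic actions taken for bleeding at any site (clip, suture, energy, topical agent). The blinded surgical team records each action by site and type on the operative record. Report the staple-line clip count as a sub-item, and report results by action type as well as in total.

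In section 9, state how this measure relates to the haemoglobin definition: whether it can by itself make a patient a bleeding case, and if so by what rule, or whether it is reported separately.

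If only clips are kept, or if operations are already complete and nothing else was recorded, limit the intra-operative conclusion to staple-line clip use. That costs nothing.

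The main change costs one form completed by a team already in theatre and already blinded. It alters what is written down, not how patients are treated. The downside is that a total of unlike actions still depends on surgeon habit, which is why the breakdown by type is needed. Suction blood loss net of irrigation could be added, but it is measured with error, adds a theatre task, and is not needed for this fix.
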